2. LIST OF ABBREVIATIONS

AMI	Acute Myocardial Infarction
██████████	██████████
CI	Confidence Interval
COPD	Chronic Obstructive Pulmonary Disease
DPC	Diagnosis Procedure Combination
ENCEP	European Network of Centres for Pharmacoepidemiology and
P	Pharmacovigilance
FDC	Fixed Dose Combination
GERD	Gastroesophageal Reflux Disease
GOLD	Global Initiative for Chronic Obstructive Lung Disease
hdPS	High Dimensional Propensity Scores
HF	Heart Failure
HR	Hazard Ratio
IBD	Inflammatory Bowel Disease
ICD	International Classification of Diseases
ICS	Inhaled Corticosteroid
IQR	Interquartile Range
IRB	Institutional Review Board
LABA	Long-Acting Beta-Agonists
LAMA	Long-Acting Muscarinic Antagonists
MDV	Medical Data Vision
MS	Multiple Sclerosis
Olo	Olodaterol
PUD	Peptic Ulcer Disease
PVD	Peripheral Vascular Disease
PS	Propensity Score
SABA	Short-acting Beta Agonist
SAMA	Short-acting Muscarinic Antagonist
SD	Standard Deviation
Tio	Tiotropium

4. ABSTRACT

Name of company: Boehringer Ingelheim			
Name of finished medicinal product: Spiolto® Respimat®; Spiriva® Respimat®			
Name of active ingredient: Tiotropium / Olodaterol fixed dose combination (ATC R03AL06); Tiotropium (ATC R03BB04)			
Protocol date: 27 Feb 2020	Study number: 1237.100	Version/Revision: 1.0	Version/Revision date: N/A
Title of study:	Early intervention effectiveness of tiotropium / olodaterol compared to tiotropium in COPD		
Rationale and background:	
Chronic obstructive pulmonary disease (COPD) is a common disease with a significant morbidity and cost burden. Long-acting muscarinic antagonists (LAMA) and long-acting beta agonist (LABA) have been the first line of treatment for COPD. Recent clinical trials have suggested that a combination of LAMA and LABA is more effective in improving lung function than their mono-components alone. The combination therapy may delay the progression to uncontrolled COPD managed with triple therapy. There is, however, limited research from real world setting showing LAMA+LABA combination therapy provides more benefit than LAMA monotherapy in Japanese patients with COPD.
 
Spiolto® Respimat®, a combination of Olodaterol (a LABA) and Tiotropium (a LAMA) (herein referred to as Tio/Olo) was approved in September 2015 in Japan. Spiriva® Respimat®, a Tiotropium (a LAMA) monotherapy (herein referred to as Tio), was approved in October 2004 in Japan.
 
This study aims to evaluate the time to escalation to triple therapy among the Japanese COPD patients newly initiating therapy with Tio or Tio/Olo using real world data.
		

Name of company: Boehringer Ingelheim			
Name of finished medicinal product: Spiolto® Respimat®; Spiriva® Respimat®			
Name of active ingredient: Tiotropium / Olodaterol fixed dose combination (ATC R03AL06); Tiotropium (ATC R03BB04)			
Protocol date: 27 Feb 2020	Study number: 1237.100	Version/Revision: 1.0	Version/Revision date: N/A
Research question and objectives:	
To compare the early intervention effectiveness of Tio/Olo vs. Tio among COPD patients.
 
To compare the early intervention effectiveness of Tio/Olo vs. Tio among COPD patients.
 
The primary objective of the study is to
 
 - Compare time to LAMA/LABA/ICS triple therapy initiation among initiators of Tio/Olo vs. initiators of Tio. 
The secondary objective of the study is to compare the following among initiators of Tio/Olo vs. initiators of Tio:
 
 - Time to First Moderate or Severe COPD Exacerbation - Number of Moderate or Severe COPD Exacerbations 
Further endpoints:
 
 - All-Cause Mortality, - Number of Unique Pulmonary Medication Prescriptions - Number of Hospitalizations for a Respiratory Condition - Major Cardiovascular Adverse Event (MACE) - Home oxygen therapy (HOT) 		
Study design:	
This will be a new-user, active comparator retrospective comparative cohort study using MDV Japan, a Japanese electronic healthcare research database. It will employ high dimensional propensity scores (hdPS) to match 1 Tiotropium initiator for each Tiotropium/ Olodaterol initiator.
		

Name of company: Boehringer Ingelheim			
Name of finished medicinal product: Spiolto® Respimat®; Spiriva® Respimat®			
Name of active ingredient: Tiotropium / Olodaterol fixed dose combination (ATC R03AL06); Tiotropium (ATC R03BB04)			
Protocol date: 27 Feb 2020	Study number: 1237.100	Version/Revision: 1.0	Version/Revision date: N/A
Population:	
The study cohort will include all patients who initiate Tiotropium/ Olodaterol (Tio/Olo) or Tiotropium (Tio) during the patient selection period (28 September 2015 to 31 December 2018). Initiation (new use) will be determined based on no prescription claims for Tio/Olo or Tio during the 180-day baseline period or during all available data prior to cohort entry date. All patients will additionally be required to have a second claim for the index medication within 60 days after cohort entry to ensure primary adherence of index therapy and regular visit to one of the MDV facilities for treatment of COPD on or any time prior to cohort entry.
 
The following exclusion criteria will then be applied to generate the unmatched cohort:
 
 ● Aged <40 years on cohort entry. ● Any LAMA, LABA, or ICS maintenance therapy (alone or in combination) during the 180-day baseline period prior to cohort entry for maintenance treatment and duration >30 days, or any prescription within the 30 days prior to cohort entry. ● Patients without continuous enrolment (days since first inpatient/ outpatient encounter in the data) during the baseline period. ● No prior diagnosis of COPD [ICD-10: J41*, J43*, J44* and doubt (UTAGAIFLG) = 0 (no)] ● Patients without a second prescription claim of their index medication within 60 days after the cohort entry date. ● Diagnosis of asthma [ICD-10: J45* and doubt (UTAGAIFLG) = 0 (no)] during the baseline period. ● Diagnosis of lung cancer [ICD-10: C34*, D02.2, Z80.1, Z85.1 and doubt (UTALAIIFLG) = 0 (no)] or lung transplant (Health claim code: 150317670, 150322510, 150322610, 150336510, 150336610, 150336710, 150399270) prior to the cohort entry date using all available data. ● Patients who initiate both Tio/Olo and Tio simultaneously on the cohort entry date. 		

Name of company: Boehringer Ingelheim			
Name of finished medicinal product: Spiolto® Respimat®; Spiriva® Respimat®			
Name of active ingredient: Tiotropium / Olodaterol fixed dose combination (ATC R03AL06); Tiotropium (ATC R03BB04)			
Protocol date: 27 Feb 2020	Study number: 1237.100	Version/Revision: 1.0	Version/Revision date: N/A

● Any use of triple therapy (LAMA + LABA + ICS) during the baseline period or between the cohort entry date and 1 day prior to the start of follow-up.
 
All patients will be selected into the first treatment arm (Tio/Olo or Tio) that they qualify for and will not be allowed to re-enter the cohort by design.
 
The cohort will then be used to construct two matched cohorts (not mutually exclusive) according to the: 1) basic propensity scores and 2) high dimensional propensity scores.
			

Name of company: Boehringer Ingelheim			
Name of finished medicinal product: Spiolto® Respimat®; Spiriva® Respimat®			
Name of active ingredient: Tiotropium / Olodaterol fixed dose combination (ATC R03AL06); Tiotropium (ATC R03BB04)			
Protocol date: 27 Feb 2020	Study number: 1237.100	Version/Revision: 1.0	Version/Revision date: N/A
Variables: 
Exposures
 
 ● Exposure: Tiotropium/Olodaterol (Spiolto®). ● Reference: Tiotropium (Spiriva®). 
Primary Outcome
 
The primary outcome of interest is time to triple therapy initiation (first event per patient) defined as any LAMA/LABA/ICS fixed dose combination or any concurrent use for 30 consecutive days of the following:
 
 ● any LAMA/LABA fixed dose combination + any ICS single formulation ● any LAMA single formulation + any LABA/ICS fixed dose combination ● any LAMA single formulation + any LABA single formulation + any ICS single formulation 
Secondary outcomes
 
 ● Time to First Moderate or Severe COPD Exacerbation ● Number of Moderate or Severe COPD Exacerbations 
Further endpoints
 
 ● All-Cause Inpatient Mortality ● Number of Unique Pulmonary Medication Prescriptions ● Number of Hospitalizations for a Respiratory Condition ● Major Cardiovascular Adverse Events (MACE) ● Home oxygen therapy (HOT) 
Covariates
 
 ● Demographics (last recorded): Age, Sex, Year of Cohort Entry, Hospital Size (as a proxy for urban/rural). ● Concomitant Medications (see detail below) 
Comorbidities/Symptoms (see detail below)
			

Name of company: Boehringer Ingelheim			
Name of finished medicinal product: Spiolto® Respimat®; Spiriva® Respimat®			
Name of active ingredient: Tiotropium / Olodaterol fixed dose combination (ATC R03AL06); Tiotropium (ATC R03BB04)			
Protocol date: 27 Feb 2020	Study number: 1237.100	Version/Revision: 1.0	Version/Revision date: N/A
Data sources:	MDV is an electronic, record-based healthcare database that spans from 01 April 2008 to 31 March 2019, and contains 25.1 million observable patients from 374 medical facilities across Japan.		
Study size:	
There are 1,829 new users of Tiotropium/Olodaterol and 13,132 new users of Tiotropium between 28 September 2015 and 31 October 2018 who satisfied the initial inclusion criteria of new use with at least 2 prescriptions for the index medication within 60 days, and excluding patients without a COPD diagnosis during the baseline period, age <40, diagnosis of asthma during the baseline period, no history of lung cancer or lung transplant, any LAMA, LABA, or ICS maintenance therapy within the 30 days prior to cohort entry, and without continuous enrolment (days since first inpatient/outpatient encounter in the data) during the baseline period.
 
Based on the result of study by Hahn B et al, it is assumed that the triple therapy initiation rate during 1 year is 6% in Tio+Olo group and 10% in Tio group. In total, 1856 patients are needed to observe 141 events and to detect the difference (HR of 1.7) with 2-sided alpha of 0.05 and 90% power.
 
After propensity score matching, it will be assessed whether sufficient number of sample size is available to detect the expected difference. If not available, the treatment difference will be explored in highly explorative manner (i.e., p-value is considered descriptively and point estimate with confidence interval is focused).
		

Name of company: Boehringer Ingelheim			
Name of finished medicinal product: Spiolto® Respimat®; Spiriva® Respimat®			
Name of active ingredient: Tiotropium / Olodaterol fixed dose combination (ATC R03AL06); Tiotropium (ATC R03BB04)			
Protocol date: 27 Feb 2020	Study number: 1237.100	Version/Revision: 1.0	Version/Revision date: N/A
Data analysis:	
 ● Descriptive analyses 
For demographic and lifestyle variables, the value recorded on the cohort entry date will be reported, otherwise the most recent known value will be reported. Presence of comorbidities and use of concomitant medication use will be determined based on whether they ever occurred within the 180-day baseline period preceding the index date. Differences in the confounder distributions will be inspected for successful confounder balance of measured characteristics.
 ● Rate of Triple Therapy Initiation 
Among the unmatched and matched cohorts, rates of triple therapy use for each treatment group will be reported as the number of events (first per patient) divided by the total number of person-years at risk during follow-up. Comparative rates and corresponding 95% CIs will be reported as both the rate ratio and rate difference per 1,000 person-years at risk.
 ● Risk of Triple Therapy Initiation 
Among the unmatched and matched cohorts, risk of triple therapy use for each treatment group will be reported as the number of events (first per patient) divided by the total number of patients at risk. Comparative risks and corresponding 95% CIs will be reported as both the risk ratio and risk difference per 1,000 person at risk.
 ● Comparative Effectiveness ● Hazard Ratio for Triple Therapy Use Initiation 
Among both the basic propensity score matched and high dimensional
		

Name of company: Boehringer Ingelheim			
Name of finished medicinal product: Spiolto® Respimat®; Spiriva® Respimat®			
Name of active ingredient: Tiotropium / Olodaterol fixed dose combination (ATC R03AL06); Tiotropium (ATC R03BB04)			
Protocol date: 27 Feb 2020	Study number: 1237.100	Version/Revision: 1.0	Version/Revision date: N/A

propensity score matched cohort, Cox regression will be used to estimate the hazard ratios and 95% CI for Tiotropium/Olodaterol compared to patients treated with Tiotropium during follow-up for time-to-first triple therapy initiation using an intention-to-treat censoring approach.
 
Sensitivity Analyses
 
 1. Less Stringent Qualifying Event Criterion 
Instead of defining the qualifying event as two prescriptions within 60 days, patients may enter on only one prescription. While some confidence is lost in whether the patients truly took their index medications, the less stringent qualifying event criterion will allow more patients to be included, increasing statistical power. Furthermore, the possibility of immortal time bias is also mitigated, since the time between prescriptions is no longer present.
 
 2. As-treated Censoring 
The analysis will use an as-treated approach for primary, secondary and further endpoint outcomes. In addition to the censoring criteria mentioned for the intention-to-treat approach (outcome, death, or end of data), patients will also be censored after medication discontinuation or switching over to the other arm.
 
 3. Alternative algorithm for COPD as exclusion criterion 
The analysis will use a different set of diagnosis codes for COPD (J43*, J44*) to identify patients with COPD. Compared to the primary analysis, this identification approach omits the diagnostic code for chronic bronchitis (J41*), as this code is commonly used by pulmonologists when prescribing Mucolytics to patients without
			

Name of company: Boehringer Ingelheim			
Name of finished medicinal product: Spiolto® Respimat®; Spiriva® Respimat®			
Name of active ingredient: Tiotropium / Olodaterol fixed dose combination (ATC R03AL06); Tiotropium (ATC R03BB04)			
Protocol date: 27 Feb 2020	Study number: 1237.100	Version/Revision: 1.0	Version/Revision date: N/A

chronic bronchitis. While some true chronic bronchitis patients may be excluded, this approach may increase specificity in identifying patients with COPD.
 
4. Asthma patients with doubt
 
Asthma patients with doubt are defined as patients with a diagnosis code for asthma and without evidence of any asthma specific treatment (ie., ICS, ICS/LABA) This sensitivity analysis will include patients identified with asthma with doubt.
 
5. Asthma-COPD Overlap Syndrome (ACOS) sensitivity analysis
 
Patients that have evidence of asthma during the follow-up period will have their data censored on the date of asthma diagnosis during the follow-up period. This will ensure that they contribute information during their COPD disease trajectory up until the time they develop asthma. This approach will mitigate introducing immortal time bias for those patients with ACOS during the follow-up period.
			

Name of company: Boehringer Ingelheim			
Name of finished medicinal product: Spiolto® Respimat®; Spiriva® Respimat®			
Name of active ingredient: Tiotropium / Olodaterol fixed dose combination (ATC R03AL06); Tiotropium (ATC R03BB04)			
Protocol date: 27 Feb 2020	Study number: 1237.100	Version/Revision: 1.0	Version/Revision date: N/A
Milestones:	
10-Sept-2019: Kickoff 16-Sept-2019: Initial Protocol Draft 18-Oct-2019: BI Review of Draft Protocol 08-Nov-2019: Revise Protocol per BI Feedback 15-Nov-2019: Protocol approval from BI 28-Feb-2020: Implement Study 14-Mar-2020: Review of preliminary results and discussion of report priorities 31-Mar-2020: Sensitivity Analysis TBD 2020: Manuscript kickoff / initial discussion with medical writing team TBD: [REDACTED] to provide manuscript outline with key results for medical writer 30-May-2020: Draft Study Report TBD-2020: BI Review of Study Report TBD-2020: Revise Report per BI Feedback
		

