9.2 SETTING

9.2.1 Definitions

Study Period: the entire period of time that includes the baseline period, the cohort entry date (index date), and follow-up period for the study population. The study period will be from **01 April 2015** (180 days prior to Spiolto approval date of 28 September 2015 in Japan) to **31 March 2019** (end of available data).

Patient Selection Period: the period of time for which patients are eligible to enter the cohort. The earliest date of the patient selection period is **28 September 2015**, (the Spiolto approval date in Japan). The latest date of the patient selection period is 31 December 2018, corresponding to 90 days before the end of available data (31 March 2019), ensuring that all patients have at least 60 days after the cohort entry date to identify a second prescription for index therapy and at least 30 days to be capable of the 30-day overlap to determine the triple therapy initiation outcome.

Cohort Entry Date: Date of entry to the initial cohort of Tio/Olo vs. Tio users (*first prescription*).

Baseline Period: the 180-day period that ends 1 day prior to the cohort entry date used to assess covariate information. The earliest start of the baseline period would be 01 April 2015, corresponding to 180 days prior to the approval date of Spiolto.

[figure not shown]
Follow-Up Period: the period starting at the second prescription for Tio/Olo or Tio within 60 days of the cohort entry date (first prescription) and ending at the earliest occurrence of the outcome (use of triple therapy), or the first occurrence of inpatient death, disenrollment, or end of the study period (31-Mar-2019). A sensitivity analysis will employ an as-treated censoring approach to further censor upon discontinuation of index therapy or initiation of the other index treatment arm. Patients may have different lengths of follow-up (i.e. variable follow-up).

Since health care is nationalized in Japan, the notion of enrollment is not applicable. Therefore, a proxy enrolment criterion defined as start of enrolment = date of first inpatient/outpatient encounter; end of enrolment = date of last inpatient/outpatient encounter will be used. “Enrolment” herein will refer to this proxy enrolment measure. For entry into the study population, patients will be required to have had at least 180 days of enrollment prior to the cohort entry date.

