9.2.2 Study population

The study cohort will include all patients who initiate Tiotropium/Olodaterol (Tio/Olo) or Tiotropium (Tio) during the patient selection period. Initiation (new use) will be determined based on no prescription claims for Tio/Olo or Tio during the baseline period or during all available data prior to cohort entry date. All patients will additionally be required to have a second claim for the index medication within 60 days after cohort entry to ensure primary adherence of index therapy.

The following exclusion criteria will then be applied to generate the unmatched cohort:

- Aged <40 years on cohort entry.

[figure not shown]
Proprietary confidential information © 2020 Boehringer Ingelheim International GmbH or one or more of its affiliated companies

- Any LAMA, LABA, ICS maintenance therapy (alone or in combination) during the 180-day baseline period prior to cohort entry for maintenance treatment and not cough, i.e. duration >30 days, or any prescription within the 30 days prior to cohort entry.
- Patients without continuous enrolment (days since first inpatient/outpatient encounter in the data) during the baseline period.
- No prior diagnosis of COPD [ICD-10: J41*, J43*, J44* and doubt (UTAGAIFLG) = 0 (no)]
- Patients without a second prescription claim of their index medication within 60 days after the cohort entry date.
- Diagnosis of asthma [ICD-10: J45* and doubt (UTAGAIFLG) = 0 (no)] during the baseline period.
- Diagnosis of lung cancer [ICD-10: C34*, D02.2, Z80.1, Z85.1 and doubt (UTALAIFLG) = 0 (no)] or lung transplant (Health claim code: 150317670, 150322510, 150322610, 150336510, 150336610, 150336710, 150399270) prior to the cohort entry date using all available data.
- Patients who initiate both Tio/Olo and Tio simultaneously on the cohort entry date.
- Any use of triple therapy (LAMA + LABA + ICS) during the baseline period or between the cohort entry date and 1 day prior to the start of follow-up.

All patients will be selected into the first treatment arm (Tio/Olo or Tio) that they qualify for and will not be allowed to re-enter the cohort by design.

The cohort will then be used to construct two matched cohorts (not mutually exclusive) according to the: 1) basic propensity scores and 2) high dimensional propensity scores

Figure 2 Depicts the flow diagram of patients.

Basic Propensity Score Matching

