Basic propensity score will be used to assess comparative effectiveness between the two exposure groups. The basic propensity score will be estimated using logistic regression with Tio/Olo treatment as the outcome and the following variables determined *a priori* as predictors:

a) predefined demographic variables (measured at time of cohort entry):

- Age
- Sex
- Calendar Year of Index
- Hospital Size (as a proxy for urban/rural)

b) all concomitant medications and comorbidities/conditions/other variables enumerated in [Section 9.3.3.](#)

The final basic propensity score will then be used to identify one initiator of *Tiotropium* for each initiator of *Tiotropium/Olodaterol* with the same propensity score (\pm a caliper of 5%) (**Austin 2011**).

High Dimensional Propensity Score Matching

In addition to the basic propensity scores, high dimensional propensity score (hdPS) analysis will also be used to assess comparative effectiveness between the two exposure comparison groups. hdPS is a modification of traditional propensity scores that incorporate additional steps for empirical variable selection. Briefly, hdPS includes additional covariates by ranking a complete list of available variables of a given attribute (e.g. all ICD-10 codes) based on prevalence, recurrence, association between covariate and exposure, and association between covariate and outcome, and then including the top covariates in that list in the propensity score prediction. This technique has been shown to produce improved effect estimates compared to using all predefined covariates in the propensity score prediction (**Schneeweiss 2009**).

The set of covariates to estimate the propensity scores will include the same predefined covariates as in the basic propensity scores (categories a and b), but also an empirically chosen set of covariates (category c):

a) predefined demographic variables (measured at time of cohort entry):

- Age
- Sex
- Calendar Year of the Cohort Entry Date
- Hospital Size (as a proxy for urban/rural)

b) all concomitant medications and comorbidities/conditions/other variables enumerated in [Section 9.3.3.](#)

c) The top variables (number of variables determined by the [REDACTED]) chosen by the hdPS algorithm described above. The following attributes will be used to select variables eligible for hdPS analysis:

- Disease Data – ICD-10 Codes
- Inpatient ACT – Health Claim Code
- Outpatient ACT – Health Claim Code
- Lab Data – Laboratory Code

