9.3.3 Covariates

The covariates listed below consist of demographics, medications, comorbidities, and other variables that are hypothesized to confound the relationship between exposure and outcome. Covariates will be identified based on data recorded within 180 days prior to or on the index date (date of

dispensing/initiation of the exposure), unless otherwise specified. If multiple measurements are made in the baseline period, then the most recent measurement will be used.

There is an additional variable for “doubt diagnosis” related to each disease diagnosis. Only confirmed diagnoses will be used for all disease variables (this represents ~95% of all diagnoses).

Absolute and relative frequencies of each covariate will also be reported. Detailed descriptions of the listed covariates can be found in Annexes 2 and 3. The measure definitions for diagnoses are subject to modification to further incorporate disease codes/names as deemed appropriate upon further exploration of the data during study implementation.

Demographics (last recorded)

- Age
- Sex
- Year of Cohort Entry
- Hospital Size (as a proxy for urban/rural).

Concomitant Medications

- Oral/Injected Corticosteroids
- Short acting beta agonist (SABA) (number of claims)
- Short acting muscarinic antagonist (SAMA) (number of claims)
- Systemic Xanthines
- Systemic Antileukotrienes
- Interleukin Inhibitors for Asthma
- Non-steroidal Respiratory Anti-inflammatories
- Opioids/Narcotics
- Systemic Antihistamines
- Oral Antibiotics for a Respiratory Condition (number of claims)
- Cough and Cold Preparations
- Diabetes Mellitus Medications, excluding Insulin
- Insulin
- Cytostatics
- Antirheumatics, Biologic
- Antirheumatics, Non-Steroidal
- Antithrombotic Agents
- Lipid-lowering Agents
- Antihypertensives/Diuretics
- Antiepileptics/Psycholeptics/Psychoanaleptics
- Antipsoriatics
- Antivirals
- Thyroid Therapies
- Vaccinations

[Antibiotics + Respiratory diagnosis, [REDACTED] can try to find antibiotics specific to respiratory conditions]

Comorbidities/Symptoms

- COPD Exacerbations (number of exacerbations)
- All-Cause Hospitalization
- Hospitalization due to Respiratory Condition
- Acute Myocardial Infarction, AMI
- Angina Pectoris
- Peripheral Vascular Disease, PVD
- Heart Failure, HF

- Hypertension
- Cardiac Arrhythmias
- Cerebrovascular Disease
- Any Cancer (except nonmelanoma skin cancer)
- Allergic Rhinitis
- Chronic Sinusitis
- Bronchiectasis
- Pneumonia
- Chronic Bronchitis

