9.4 DATA SOURCES

The proposed study will utilize data from Medical Data Vision (MDV).

MDV is an electronic, record-based healthcare database that spans from April 1, 2008 to 31 March 2019, and contains 25.1 million observable patients. It contains patient-level information on demographics, diagnoses and prescription information from 374 medical facilities across Japan. The distribution of patients in the database is similar to that of the national demographics for patients seeking healthcare, although the MDV database has more elderly and sicker patients.

The Japanese health care structure enables anyone to seek medical treatment at any facility of their choosing, including hospitals. Thus, acute hospitals in Japan consist of both primary (outpatient) and secondary (inpatient) care facilities. In fact, the MDV database is built out of more than 80% outpatient data, which allows for identification of patients who visit hospitals without severe conditions. These hospitals follow a diagnosis procedure combination (DPC) billing structure unique to Japan that enables capture of inpatient discharge summary

information (disease name, operations, adjuvant treatment, etc.), health claims for procedures (surgery information, departments, wards, etc.), and health claims for treatments (medications, medical devices, devices, etc.). A smaller subset of consenting hospitals also provide data on blood test results.

Thus, it is expected that 1) patients with COPD in these hospitals provide a good representation of the general Japanese COPD population; and 2) data from patients treated in the different hospitals cannot be linked. Due to the nature of the database, inclusion criteria to ensure that the patients are treated for COPD in the same hospitals continuously are defined as described in [Section 9.2.2](#).

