9.12 BIAS

In principle, electronic pharmacy dispensing records are considered accurate because pharmacists fill prescriptions with little room for interpretation, and are reimbursed by insurers based on detailed, complete, and accurate claims submitted electronically (Levy 2003; Sternbach 1988). Pharmacy dispensing information is usually seen as the gold standard of drug exposure information compared to self-reported information or prescribing records in medical records.

The population-based nature of the database will avoid selection bias and ensure external validity. Confounding bias through observable covariates will be controlled for by the design, which includes propensity score matching. Specifically, compared to traditional propensity

score matching, high dimensional propensity scores will be used to reduce overfitting while retaining baseline covariate balance in matched groups (**Schneeweiss 2009**).

To minimize misclassification of the recorded patient characteristics, previously validated algorithms or code lists will be used whenever available. Code lists will be reviewed by the qualified medical reviewers prior to implementation. Basic plausibility checks will be implemented for continuous variables (e.g. age, etc.).

The covariates chosen in [section 9.3.3](#) are hypothesized to be confounders in the relationship between exposure and outcome. The range and quantity of variables selected are aimed to make the two exposure groups more comparable so that the effect estimates may more readily have a causal interpretation.

COPD patients who start on Spiriva® Respimat® may be different than Spiolto® Respimat® initiators in the clinical course and severity of COPD. Use of propensity score matching aim to reduce bias due to confounding. The addition of covariates chosen by hDPS will further aid in reducing bias by empirically selecting for strong confounders. However, it is possible that inclusion of some variables may introduce rather than remove bias (i.e. as collider bias or M-bias). Nevertheless, such biases are demonstrated to be minor, and inclusion of variables preceding exposure are generally thought to improve rather than degrade validity (**Rassen 2011**).

The requirement of second fill for inclusion in the study could lead to immortal time bias. However, as the follow-up will begin after the second fill rather than at the cohort entry date, this requirement is unlikely to bias the findings.

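### Neither propensity score has a predefined covariate for whether the index drug was started in hospital or as an outpatient, and the covariate window is stated inconsistently

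*Combined protocol and SAP*

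**What the plan says.** **Eligibility.** Section 9.2.2 opens the cohort without regard to setting: "The study cohort will include all patients who initiate Tiotropium/Olodaterol (Tio/Olo) or Tiotropium (Tio) during the patient selection period". None of the exclusion criteria limits entry to outpatient starts.

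**Score content.** Under Covariates, the Abstract gives "Demographics (last recorded): Age, Sex, Year of Cohort Entry, Hospital Size (as a proxy for urban/rural"). Section 9.2.2 puts the same four items in both scores and adds "b) all concomitant medications and comorbidities/conditions/other variables enumerated in" section 9.3.3. That list includes all-cause hospitalization, "Hospitalization due to Respiratory Condition", "COPD Exacerbations (number of exacerbations"), oral or injected corticosteroids, counts of respiratory antibiotic claims, and pneumonia. The high dimensional score (hdPS) may add inpatient and outpatient claim codes, chosen by ranking, and service-intensity variables.

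**Data.** Section 9.4 says that "the MDV database is built out of more than 80% outpatient data" and that inpatient discharge information is captured as well. Section 9.2.2 lists inpatient and outpatient claim codes as separate hdPS attributes.

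**Window.** Section 9.2.1 defines the baseline period as "the 180-day period that ends 1 day prior to the cohort entry date used to assess covariate information". Section 9.3.3 also looks back 180 days but includes the index date.

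**Severity.** Section 9.12 accepts that patients starting tiotropium (Tio) alone may differ from tiotropium/olodaterol (Tio/Olo) "initiators in the clinical course and severity of COPD", and relies on matching to deal with it.

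**The concern.** A patient given a first maintenance inhaler during a respiratory admission is plausibly sicker at that moment than one given it at a routine clinic visit, and plausibly more likely to escalate to triple therapy, exacerbate, be readmitted or die. If the share of in-hospital starts differs between Tio/Olo and Tio after matching, the primary hazard ratio and most other endpoints carry that difference.

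This is not the unmeasured confounding that section 9.9 concedes, because setting should be derivable from records the study already holds. As planned, it is neither required in the scores nor tabulated, and no analysis examines it. Good standardized differences on the listed covariates would therefore not show that the arms are alike on setting.

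**Working it through.** The plan contains no figure on this point to reproduce. The check is a reading of the specifications side by side, followed by an illustration on assumed inputs.

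**1. Is setting recorded anywhere in the scores or analyses?**

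| Place | Content | Setting of the index prescription? |
|---|---|---|
| 9.2.2, demographics | Age, sex, calendar year, hospital size | No; hospital size is described as an urban/rural proxy |
| 9.3.3, medications | Includes steroids, short-acting bronchodilators, respiratory antibiotics | No; correlates only |
| 9.3.3, comorbidities | Includes hospitalizations, exacerbation count, pneumonia | No; no timing relative to index is listed |
| 9.2.2, hdPS | Inpatient and outpatient codes, intensity quartiles | Not guaranteed; candidates only, and not tied to the index prescription |
| 9.7.2 | No subgroup analysis | No |
| 9.7.3 | Five sensitivity analyses | None separates in-hospital starts |

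The basic-score cohort, which section 9.7.1.3 also analyses for the hazard ratio, has no hdPS codes at all.

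**2. Would an admission at index be counted?**

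- 9.2.1: the window stops the day before entry, so an admission starting on the index date falls outside it.
- 9.3.3: the index date is included, so the same admission falls inside.
- Abstract (Data analysis) and 9.7.1.1: presence of comorbidities and medication use is judged over the period before entry, but these passages govern descriptive reporting.

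Under the first reading the admission is lost. Under the second it is counted, but nothing listed separates it from an admission months earlier.

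**3. How large could the effect be?** The documents give neither the share of in-hospital starts by arm nor its effect on the hazard, so every input here is assumed. Let p1 and p0 be the shares in Tio/Olo and Tio that remain after matching, and g the hazard multiplier for an in-hospital start given the other covariates. The hazard ratio (Tio/Olo relative to Tio) is then multiplied by approximately

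[1 + p1(g − 1)] / [1 + p0(g − 1)].

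| g | p1 = 0.25, p0 = 0.15 | Shares reversed |
|---|---|---|
| 1.5 | 1.125/1.075 = 1.05 | 0.96 |
| 2 | 1.25/1.15 = 1.09 | 0.92 |
| 3 | 1.50/1.30 = 1.15 | 0.87 |

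For scale, at the 141 events planned in section 9.5, split about evenly, the standard error of the log hazard ratio is about √(4/141) = 0.168. A factor of 1.09 is then ln(1.087)/0.168 ≈ 0.5 standard errors, and 1.15 is ln(1.154)/0.168 ≈ 0.85.

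**4. Is there room to match exactly on setting?** Section 9.5 gives 13,132 Tio and 1,829 Tio/Olo new users, and 13,132/1,829 = 7.2. This is the overall ratio. The ratio among in-hospital starts is not given.

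**The case against.** The strongest reply is that the scores already carry much of this information. An admission for acute COPD would usually register on several covariates at once: all-cause and respiratory hospitalization, the exacerbation count (section 9.3.2.2 defines severe exacerbations by hospitalization), steroids, antibiotics and pneumonia. The hdPS can add inpatient codes and service intensity. This stands. It shrinks any residual imbalance and the hazard multiplier that matters, so inputs taken from crude comparisons would overstate the effect.

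A reader might also infer four stronger things that the documents do not support:

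- *That an admission starting on the index date is always missed.* Section 9.3.3, which the scores refer to, includes the index date. What can be shown is a contradiction with 9.2.1.
- *That a current admission is certainly coded the same as an old one in the scores.* The ever/never wording concerns descriptive reporting, and 9.3.3 refers detailed definitions to Annexes 2 and 3, which are not in the text available. The claim is limited to the variables as listed.
- *That the balance table is blind to the problem.* Section 9.7.1.1 reports standardized differences for the 9.3.3 variables, so close correlates are visible. Setting itself is not.
- *That pairing an in-hospital starter with an outpatient starter is itself an error.* Propensity matching balances groups, not pairs. What matters is the distribution of setting between the matched arms.

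Finally, nothing in the documents shows that the arms differ by setting. That limits what can be claimed about bias, but it is also a reason to tabulate the variable.

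**Conclusion.** The gap is real: in-hospital starts are eligible, no predefined covariate in either score records setting, and no planned analysis separates those starts. The listed proxies close part of it. The contradictory window leaves open whether an admission on the index date is counted at all.

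The documents do not support saying that the primary hazard ratio is biased, or in which direction. The factors of 1.05 to 1.15, or 0.96 to 0.87, rest on assumed shares and hazard multipliers and apply only to imbalance remaining after matching on the listed covariates. This is an inexpensive improvement against a severity difference that section 9.12 itself anticipates. It is not a demonstrated flaw in the result.

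**What to change.** 1. Add the setting of the index prescription (inpatient or outpatient) to section 9.3.3, to both propensity scores and to the balance table with its standardized difference.
2. Match exactly on setting if enough pairs remain. First tabulate the ratio of Tio to Tio/Olo among in-hospital starts, since the overall 7.2 to 1 does not establish it.
3. Add an indicator for an index prescription issued during, or within 30 days after, an admission. Classify the admission as respiratory only from information recorded by the index date. Section 9.4 says disease names come from discharge summaries, so for an admission still under way the label could otherwise be assigned after treatment started.
4. State one covariate window and use it in the Abstract, 9.2.1, 9.3.3 and 9.7.1.1, saying explicitly whether the index date is included and whether the same window applies to hdPS codes.

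The cost is a small amount of programming, a re-run of both matches and possibly some lost pairs if setting is matched exactly.
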